### Aims & Hypotheses:

**Aim 1:** To determine the impact of increased frequency and intensity of PT services compared to the usual care PT on discharge disposition of patients post-stroke.

**Hypothesis 1:** We hypothesize that patients receiving an increased frequency of PT services will have higher rate of discharging to home/acute rehabilitation center than to a subacute rehabilitation/skilled nursing facility compared to patients in the usual care PT group.

**Aim 2:** To determine the impact of increased frequency and intensity of PT services, as opposed to usual care, on functional mobility.

**Hypothesis 2:** We hypothesize that patients in the treatment physical therapy group will demonstrate higher degree of improvement on the Activity Measure for Post Acute Care (AMPAC) and Postural Assessment Stroke Scale (PASS) from admission to time of discharge from the hospital and at 90-day follow up. We also expect lower overall Modified Rankin Scale (mRS) scores for the increased frequency PT group compared the usual care PT group at three months post stroke.

**Aim 3:** To ensure that high frequency dosage is safe and feasible to implement the proposed PT regimen in the acute inpatient setting.

**Hypothesis 3:** We hypothesize that there will be fewer adverse events experienced by patients in the increased frequency compared to the usual care group.

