#### **4.0 Study Endpoints**

Physical Performance and Functional Measures: PASS scores & AMPAC scores on evaluation, day three, discharge, and 90 day follow up. Discharge disposition recommended vs ultimate discharge disposition, hospital length of stay, and 30-day readmission.

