Precaution will be taken to lessen the probability of risks; despite increased frequency of treatments, duration of upright will still be approached cautiously within the first 24 hours s/p stroke for cerebral perfusion. ALL stroke patients will be returned to supine within 24 hours post stroke and maintain head of bed <30 degrees except for medication, meals, and therapy. Therapy will be stopped if patient deemed medically unstable for increased frequency of treatments by the Stroke NP, Attendings, Fellow, or PI; this decision will be documented via "bed rest" orders in the patient's electronic medical chart, so that the study team is aware to avoid progressive frequent upright mobilization.

**Data collection:** Patient data will be collected from their medical record. Data collected from EPIC/patient's MUSC EMR will be coded in the research database. Data collected include:

- 1) Demographics: sex, age, race
- 2) Stroke risk factors: history of HTN, HLD, A-fib, or DM
- 3) Stroke specifics: type of stroke (hemorrhagic vs ischemic), location of stroke, stroke severity (measured by NIHSS & MRS), time of symptoms to presentation, intervention (tPA or thrombectomy) and complications
- 3) Physical Performance and Functional Measures: Postural assessment stroke scale scores on evaluation, day three and 90 day follow up. Discharge disposition recommended vs ultimate discharge disposition, hospital length of stay.

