For the primary outcome, PASS, to test the null hypothesis of no difference between the group versus a MCID of 2.7, at 5% significance level, using a repeated measure designs at 4 time points and an autoregressive correlation of .6, and a standard deviation of 720 with more than 80% power. Although there is power to detect a moderately small difference (2.7 as mentioned), the purpose here is also to estimate the difference between the two randomized groups. Based on the past literature, in similar populations the standard deviation of PASS measurements is at the most 7.20 Using this, with a sample of 75 patients in each group, with 95% confidence at the end of the study we can estimate this difference within a margin of error of 2.3.

We are planning to conduct the analysis using intention to treat paradigm. In a preliminary analysis we will compute all summary statistics. Initial plots, such as spaghetti plots, will be used to guide our analyses. A general linear mixed model approach will be used to analyze all the outcomes. This model will account for the correlations between time points using either a compound symmetric or spatial structure for the covariance matrix. Post-hoc analyses using Tukey type adjustments will be performed to obtain least squares estimates of the differences between the two randomized groups. Although the study is powered based on only the primary outcome (PASS), we will apply multiple comparisons adjustments for the rest of the outcomes, using Bonferroni corrections. We will test for the assumptions using diagnostic procedures and take appropriate actions if needed. Also, we will define an outcome to be 'favorable' or 'unfavorable' based on a threshold and apply generalized linear mixed models with logistic link and repeat the analyses. We will attempt to minimize drop- outs but in case of missing data, we will assume Missing at Random or Missing Completely at Random. If necessary we will perform multiple imputations. For all analyses, we will use SAS, (MIXED, GLIMMIX, MI and MIANALYZE).

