## **12.0 Withdrawal of Subjects:**

Subjects will be withdrawn from the research without their consent with the occurrence of worsening medical status, medical instability that limits ability to progress mobility or transfer to the ICU. For subjects who request to withdraw from the research trial, investigators may retain and analyze already collected data relating to that subject.

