## **13.0 Risks to Subjects:**

Early mobilization in the acute stroke population may pose risks including but not limited to falls, decreased cerebral perfusion, worsening weakness and/or worsening stroke. The research team will monitor blood pressures before each PT session to make sure it is safe for the individual to participate. A confidentiality breach is also a risk associated with this research. However, no paper records will be stored or reviewed other than consent forms and only coded data will be used for the analysis. Identifying information will be removed from the primary database. Identifying information will be stored in a separate file with a unique identifier assigned to the patient to link the two datasets.

The treatment you receive may prove to be less effective or to have more side effects than the other study treatment(s) or other available treatments. The experimental treatments may have unknown side effects. The researchers will let you know if they learn anything during the course of the study that might make you change your mind about participating in the study.

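### Section 12.0 withdraws deteriorating patients from the research, not only from study therapy, and the plan provides no outcome collection afterwards, which conflicts with its intention-to-treat analysis

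*Combined protocol and SAP*

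**What the plan says.** Section 12.0 gives the rule: "Subjects will be withdrawn from the research without their consent with the occurrence of worsening medical status". The other triggers are "medical instability that limits ability to progress mobility or transfer to the ICU". The section's only sentence about data concerns patients who themselves ask to leave; it lets investigators keep what was collected before that. It says nothing about data on patients whom the investigators withdraw.

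Section 10.0 has a separate rule that stops treatment: "Therapy will be stopped if patient deemed medically unstable for increased frequency of treatments by the Stroke NP, Attendings, Fellow, or PI". It works through bed rest orders and is silent on follow-up.

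On analysis, Section 11.0 says: "We are planning to conduct the analysis using intention to treat paradigm". On gaps in the data it says: "in case of missing data, we will assume Missing at Random or Missing Completely at Random". Multiple imputation is to be used if needed.

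Section 4.0 schedules "PASS scores & AMPAC scores on evaluation, day three, discharge, and 90 day follow up". Section 10.0 lists PASS at evaluation, day three and 90 days only.

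Section 13.0 says that early mobilisation "may pose risks including but not limited to falls, decreased cerebral perfusion, worsening weakness and/or worsening stroke". Hypothesis 3 in Section 1.0 expects that "there will be fewer adverse events experienced by patients in the increased frequency compared to the usual care group".

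**The concern.** The triggers are part of the patient's course after randomisation and are closely tied to outcome. They also overlap the harms that Section 13.0 attributes to early mobilisation. If the rule is followed as written, patients who deteriorate leave the study and those who do well stay. An intention-to-treat comparison needs outcomes on everyone randomised, whatever happened to their therapy.

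Three things are at stake:

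- **Primary outcome.** PASS and AMPAC after withdrawal are lost in the patients whose scores are likely to be poorest.
- **Missing-data assumption.** Missingness triggered by worsening is not completely at random. It is missing at random only if the recorded data explain it.
- **Aim 3.** The event that triggers withdrawal can be recorded (Section 7.0 has adverse events entered in the chart and research record). Later events in the same patient need not be. The safety review after every 25 patients looks only at data already collected.

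**Working it through.** **1. Does the text stop observation, or only therapy?**

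- Section 12.0 is mandatory and refers to the research.
- Section 10.0 stops therapy for instability. It neither keeps such patients in follow-up nor overrides Section 12.0. Its wording refers to the increased frequency of treatment, so it does not clearly cover usual care.
- Section 7.0 lists the ICU as a study setting, yet Section 12.0 makes a move there a reason to withdraw.
- No section provides for outcome collection after an investigator-initiated withdrawal.

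**2. What is lost?** Take a patient withdrawn before day three.

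- PASS: three of four values under Section 4.0, or two of three under Section 10.0.
- AMPAC: three of four values under Section 4.0.
- Disposition, length of stay, mRS and adverse events: Sections 7.0 and 10.0 place these in the medical record, so they may exist. Whether they may be used after withdrawal is not stated.

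**3. Does the analysis plan repair it?** This patient's only PASS was taken before the deterioration. A mixed model would predict the 90-day value from that score and from patients who stayed. Imputation could use the complications recorded under Section 10.0, but the plan names no such variables and no sensitivity analysis for departures from missing at random. Adverse events that were never collected cannot be recovered reliably by imputation.

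**4. The plan's own figures.** Inputs: 75 per arm, difference 2.7, four time points, autoregressive correlation 0.6, 5% level (two-sided assumed). The SD is 7 (Section 6.0, taking the 20 as a citation mark) or 7.2 (if Section 11.0 is read as a decimal).

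- Margin of error = 1.96 × SD × √(2/75) = 2.24 (SD 7) or 2.30 (SD 7.2). The stated 2.3 reproduces with 7.2.
- Variance factor for the mean of four measures = [4 + 2(3×0.6 + 2×0.36 + 0.216)]/16 = 0.592. Power is then 86.6% (SD 7) or 84.7% (SD 7.2), so the stated power above 80% reproduces.
- A single time point gives 65.6% or 63.2%.

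**5. Illustration of bias.** Let p be the proportion withdrawn after the first PASS, and d the number of points by which their true 90-day value falls below the model's prediction. T is the experimental arm and C is usual care. The bias in the T minus C difference is pT×dT − pC×dC. The document gives none of these inputs; all are assumed. With the same d in both arms:

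| Withdrawal, T v C | d = 3.5 | d = 7 | d = 10 |
|---|---|---|---|
| 10% v 10% | 0 | 0 | 0 |
| 10% v 5% | 0.18 | 0.35 | 0.50 |
| 15% v 5% | 0.35 | 0.70 | 1.00 |

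The largest entry is 1.00/2.7 = 37% of the planned difference. If the primary contrast is instead the mean of four measures, with the first observed and the full gap at the other three, it is 1.00 × 3/4 = 0.75, or 28%. Section 11.0 does not say which contrast is primary.

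The equal-d condition matters:

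- Equal withdrawal can still give bias. At 10% in each arm with dT = 10 and dC = 3.5, bias = 1.00 − 0.35 = 0.65.
- The direction can reverse. At 10% v 5% with dT = 3.5 and dC = 10, bias = 0.35 − 0.50 = −0.15.

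**6. Precision.** The 150 carries no stated allowance for attrition. If 20% contributed no data (60 per arm), the power in step 4 would fall to 76.1% (SD 7.2) or 78.4% (SD 7). That overstates the loss, because withdrawn patients would usually have a first PASS.

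**The case against.** The strongest reply is that silence is not prohibition. Section 12.0 does not say that outcome data stop. Its triggers largely concern fitness to mobilise, Section 11.0 promises intention to treat and an effort to limit drop-out, and Section 10.0 already stops therapy alone. The authors may have meant only the end of study mobilisation. That is possible, but staff follow the text, and the text ends research participation with nothing to say that follow-up continues. Ambiguity on this point still needs an amendment.

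A reader might infer that Aim 1 disposition and the 90-day mRS would be lost as well. The document does not support that. These are to come from the chart and may exist without a research assessment; what is missing is a statement that they may be used.

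It is also fair that unequal withdrawal is not shown. Section 12.0 has no arm-specific wording, both arms receive physical therapy, and the return to supine in the first 24 hours applies to all. More sessions, each preceded by a blood pressure check, give more occasions to detect instability in the experimental arm. That makes a difference plausible but does not establish one.

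Finally, Sections 5.0 and 9.0 require personal capacity and signed consent, and no surrogate route is described. A patient who worsens may lose capacity, so the remedy needs more than one sentence in Section 12.0. This objection stands, and the fix allows for it.

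**Conclusion.** The point holds. As written, Section 12.0 removes patients from observation for reasons tied to outcome and to the harms under study, and nothing elsewhere restores their follow-up. That conflicts with the intention-to-treat plan, makes missing at random doubtful and missing completely at random untenable for these patients, and can leave later adverse events out of the Aim 3 comparison. The firm loss is PASS and AMPAC after withdrawal.

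The size and direction of any bias are unknown. The 0 to 1.0 points at 90 days is an illustration resting on assumed withdrawal of up to 15% v 5% and an equal gap of up to 10 points in both arms; it is not a bound. A reader might infer that the rule flatters the experimental regimen or hides its harm. The document does not support that: it gives no withdrawal rates by arm, and the direction depends on the gaps as well as the rates.

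This should be amended, because outcomes not collected cannot be recovered later.

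**What to change.** Amend Section 12.0 as follows:

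- Worsening, instability or ICU transfer pauses or stops study therapy only, by clinical judgement, with wording that covers both arms and agrees with the stopping rule in Section 10.0.
- PASS, AMPAC, mRS, disposition, length of stay, 30-day readmission and adverse events continue to be collected to day 90 for every randomised patient unless consent is withdrawn. Where a patient is too ill for PASS or AMPAC, collect the chart-based outcomes.
- The consent form states that follow-up continues after therapy stops, including if capacity is lost, as the IRB allows.
- The date and reason for stopping therapy are recorded in both arms.

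The cost is a wording and consent amendment, one data field, and follow-up of what should be a few sicker patients at visits already planned; 90-day follow-up may already be virtual. Some PASS values will still be missing. The clinical protection is unchanged, since therapy still stops when it should.

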## **13.0 Risks to Subjects:**

Early mobilization in the acute stroke population may pose risks including but not limited to falls, decreased cerebral perfusion, worsening weakness and/or worsening stroke. The research team will monitor blood pressures before each PT session to make sure it is safe for the individual to participate. A confidentiality breach is also a risk associated with this research. However, no paper records will be stored or reviewed other than consent forms and only coded data will be used for the analysis. Identifying information will be removed from the primary database. Identifying information will be stored in a separate file with a unique identifier assigned to the patient to link the two datasets.

The treatment you receive may prove to be less effective or to have more side effects than the other study treatment(s) or other available treatments. The experimental treatments may have unknown side effects. The researchers will let you know if they learn anything during the course of the study that might make you change your mind about participating in the study.

## **14.0 Potential benefits to subjects or others:**

The potential benefit to patient's is that the treatment they receive may prove to be more effective than the other study treatment or than other available treatments, although this cannot be guaranteed. This treatment may increase a patient's independence and may lead to a shorter hospital length of stay and improved functional mobility outcomes (ie: regaining the ability to stand and walk).

It is hoped that the information gained from the study will help in the treatment of future patients with similar conditions and that it will help the researcher learn more about physical therapy approach to mobility post stroke

## **15.0 Sharing of results with subjects:**

Results of the study will not be shared with the individual subjects.

